3.4.1 Dose Modification Guidelines for Trametinib Adverse Events of Special Interest

The dose levels for this study are provided in Table 1.

Dose Levels	Trametinib once daily
Full dose	2 mg
1 st Dose reduction	1.5 mg
2 nd Dose reduction	1.0 mg

Table 1 Dose Level Reduction Guidelines

3.4.2 If an AE resolves to grade 1 or lower (or baseline) and remains grade 1 or lower at the reduced dose level and the subject does not experience any additional AEs requiring dose hold or reductions, then after 4 weeks of the study treatment at reduced dose, the dose of trametinib may be increased one dose level. If a dose reduction below 1 mg once daily for trametinib is required, then trametinib will be permanently discontinued.

3.4.3 Guidelines for Cardiovascular Adverse Events

Cardiovascular adverse events have been seen in subjects receiving trametinib[4]). Guidelines for LVEF decreases and hypertension are provided below.

3.4.3.1 Left Ventricular Ejection Fraction (LVEF)

Decreases of the left-ventricular-ejection-fraction (LVEF) have been observed in subjects receiving trametinib. Therefore, ECHOs (preferred) or MUGA's must be performed to assess cardiac ejection fraction. The procedure performed at baseline must be performed at all designated visits as outlined in the Time and Events Table (See Section [4.1](#)).

Dose modification guidance and stopping criteria for LVEF decrease are provided (Table 2).

Table 2 Dose Modification Guidelines and Stopping Criteria for LVEF Decrease

Clinic	LVEF-drop (%) or CTCAE grade	Action and Dose Modification
Asymptomatic	Absolute decrease of >10% in LVEF compared to baseline and ejection fraction below the institution's LLN	
 • Interrupt trametinib and repeat ECHO/MUGA within 2 weeks^a • If the LVEF recovers within 4 weeks (defined as LVEF ≥ LLN and absolute decrease ≤ 10% compared to baseline): 
 - Consult with the subprotocol Study Chair and request approval for restart - Restart treatment with trametinib at reduced dose by one dose level^b - Repeat ECHO/MUGA 2, 4, 8 and 12 weeks after re-start; continue in intervals of 12 weeks thereafter • If LVEF does not recover within 4 weeks 
 - Consult with cardiologist - Permanently discontinue trametinib - Report as SAE - Repeat ECHO/MUGA after 2, 4, 8, 12, and 16 weeks or until resolution - Consult with the subprotocol Study Chair.^c
Symptomatic ^b	Grade 3: resting LVEF 39-20% or > 20% absolute reduction from baseline	
 • Permanently discontinue trametinib. • Report as SAE • Consult with cardiologist • Repeat ECHO/MUGA after 2, 4, 8, 12, and 16 weeks or until resolution
	Grade 4: resting LVEF < 20%	

Rev. Add13

Abbreviations: CTCAE = Common Terminology Criteria for Adverse Events; ECHO = echocardiogram; GSK = GlaxoSmithKline; LLN = lower limit of normal; LVEF = left ventricular ejection fraction; MUGA=Multi-gated acquisition

- If ECHO/MUGA does not show LVEF recovery after 2 weeks, repeat ECHO/MUGA 2 weeks later.
- Escalation of trametinib to previous dose level can be considered if LVEF remains stable for 4 weeks after restarting of trametinib. Approval from the subprotocol Study Chair is required.
- Symptoms may include: dyspnea, orthopnea, and other signs and symptoms of pulmonary congestion and edema.

3.4.3.2 Hypertension

Increases in blood pressure (BP) have been observed in patients receiving trametinib. Recommendations for BP monitoring and management are provided below.

Monitoring: All BP assessments should be performed under the following optimal conditions:

- The subject has been seated with back support, ensuring that legs are uncrossed and flat on the floor
- The subject is relaxed comfortably for at least 5 minutes

- Restrictive clothing has been removed from the cuff area and the appropriate right size has been selected
- The subject's arm is supported so that the middle of the cuff is at heart level
- The subject remains quiet during the measurement.
- In subjects with an initial BP reading within the hypertensive range, a second reading should be taken at least 1 minute later, with the two readings averaged to obtain a final BP measurement. The averaged value should be recorded in the eCRF.
- Persistent hypertension is defined as an increase of systolic blood pressure (SBP) > 140 mm Hg and/or diastolic blood pressure (DBP) > 90 mm Hg in three consecutive visits with blood pressure assessments from two readings as described above. Visits to monitor increased blood pressure can be scheduled independently from the per-protocol visits outlined in the study calendar. Ideally, subsequent blood pressure assessments should be performed within one week.

Table 3 Management and Dose Modification Guidelines for Hypertension

Management and Trametinib Dose Modification for Hypertension		
Event	Management Guideline	Dose Modification

Definitions used in the table:
 
 - Persistent hypertension: Hypertension detected in two separate readings during up to three subsequent visits. - Well-controlled hypertension: Blood pressure of SBP ≤140 mmHg and DBP ≤90 mmHg in two separate readings during up to three subsequent visits. - Symptomatic hypertension: Hypertension associated with symptoms (e.g., headache, light-headedness, vertigo, tinnitus, episodes of fainting or other symptoms indicative of hypertension) that resolve after the blood pressure is controlled within the normal range. - Asymptomatic hypertension: SBP > 140 mmHg and/or DBP >90 mmHg in the absence of the above symptoms. 		

(Scenario A) Asymptomatic and persistent SBP of ≥ 140 and < 160 mmHg, or DBP ≥ 90 and < 100 mmHg, or Clinically significant increase in DBP of 20 mmHg (but still below 100 mmHg).
	
 • Adjust current or initiate new antihypertensive medication(s). • Titrate antihypertensive medication(s) during the next 2 weeks to achieve well-controlled BP. If BP is not well-controlled within 2 weeks, consider referral to a specialist and go to scenario (B). 	
Continue trametinib at the current dose.

Management and Trametinib Dose Modification for Hypertension		
Event	Management Guideline	Dose Modification

(Scenario B) Asymptomatic SBP ≥160 mmHg, or DBP ≥100 mmHg, or Failure to achieve well-controlled BP within 2 weeks in Scenario A.
	
 Adjust current or initiate new antihypertensive medication(s). Titrate antihypertensive medication(s) during the next 2 weeks to achieve well-controlled BP. 	
 Interrupt trametinib if clinically indicated. Once BP is well-controlled, restart trametinib reduced by one dose level.^a

(Scenario C) Symptomatic hypertension or Persistent SBP ≥ 160 mmHg, or DBP ≥ 100 mmHg, despite antihypertensive medication and dose reduction of trametinib
	
 Adjust current or initiate new antihypertensive medication(s). Titrate antihypertensive medication(s) during the next 2 weeks to achieve well-controlled BP. Referral to a specialist for further evaluation and follow-up is recommended. 	
 Interrupt trametinib. Once BP is well-controlled, restart trametinib reduced by one dose level.^a

(Scenario D) Refractory hypertension unresponsive to above interventions or hypertensive crisis.
	Continue follow-up per protocol.	Permanently discontinue trametinib.

a. Escalation of trametinib to previous dose level can be considered if BPs remain well controlled for 4 weeks after restarting of trametinib. Approval from the subprotocol Study Chair is required.

3.4.4 Guidelines for Visual Changes

Trametinib is known to be associated with visual adverse events. An ophthalmologist should be consulted if changes in vision develop. However, if the visual changes are clearly unrelated to study treatment (e.g., allergic conjunctivitis), then monitor closely as it may be reasonable to defer ophthalmic examination. Special attention should be given to retinal findings (e.g., retinal pigment epithelial detachment (RPED) or retinovascular abnormalities (i.e., branch or central retinal vein occlusions [RVO])).

The ophthalmology exam will include best corrected visual acuity, visual field examination, tonometry, slit lamp biomicroscopic examination, and indirect funduscopy. Optical coherence tomography is recommended at scheduled visits and if retinal abnormalities are suspected. Other types of ancillary testing including visual field examination, fundus photography, and fluorescein angiography may also be indicated as determined by clinical exam.

Guidelines regarding event management and dose reduction for visual changes considered to be related to study treatment are provided in Tables 4 and 5.

Table 4 Management and Dose Modification Guidelines for Visual Changes and/or Ophthalmic Examination Findings

CTCAE Grade ^{a,c}	Adverse Event Management	Action and Dose Modification
Grade 1 ^b	
 Consult ophthalmologist within 7 days of onset 	
 If dilated fundus examination cannot be performed within 7 days of onset, interrupt trametinib until RPED and RVO can be excluded by retina specialist/ophthalmologist. If RPED and RVO excluded, continue/or restart trametinib at same dose level If RPED suspected or diagnosed: see RPED dose modification table below (following this table); report as SAE. If RVO diagnosed: Permanently discontinue trametinib and report as SAE.
Grade 2 and Grade 3	
 Consult ophthalmologist immediately 	
 Hold trametinib If RPED and RVO excluded, restart trametinib at same dose level after visual AE is ≤ grade 1. If no recovery within 4 weeks, discontinue trametinib. If RPED diagnosed, see RPED dose modification table below; report as SAE. If RVO diagnosed: Permanently discontinue trametinib and report as SAE.
Grade 4	
 Consult ophthalmologist immediately Report as SAE 	
 Hold trametinib If RPED and RVO excluded, may restart trametinib at same or reduced dose after discussion with the subprotocol Study Chair If RVO or RPED diagnosed, permanently discontinue trametinib

Abbreviations: RPED = retinal pigment epithelial detachment; CTCAE = Common Terminology Criteria for Adverse Events;
RVO= retinal vein occlusion; SAE = serious adverse event

a. Refers to CTCAE Version 4.0 ‘Eye disorders – Other, specify’
b. If visual changes are clearly unrelated to study treatment (e.g., allergic conjunctivitis), monitor closely but ophthalmic examination is not required.
c. Refers to CTCAE Version 4.0 ‘Retinopathy’

Table 5 Recommended dose modifications for trametinib for retinal pigment epithelial detachments (RPED)^a

CTCAE Grade	Action and Dose Modification
Grade 1 RPED (Asymptomatic; clinical or diagnostic observations only)	
 Continue treatment with retinal evaluation monthly until resolution. If RPED worsens follow instructions below
Grade 2-3 RPED (Symptomatic with mild to moderate decrease in visual acuity; limiting instrumental ADL)	
 Interrupt trametinib Retinal evaluation monthly If improved to ≤ Grade 1, restart trametinib at lower dose (reduced by 0.5 mg) or discontinue in patients taking trametinib 1 mg daily If no recovery within 4 weeks, permanently discontinue trametinib

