3.4 Dose Modifications

NOTE: Patients who interrupt trametinib for > 2 weeks will be removed from this subprotocol, unless the interruption was for reduction in LVEF, visual changes or RPED with subsequent recovery as described in corresponding tables below.

All toxicity grades below are described using the NCI Common Terminology Criteria for Adverse Events (CTCAE) version 4.0.

All appropriate treatment areas should have access to a copy of the CTCAE version 4.0. A copy of the CTCAE version 4.0 can be downloaded from the CTEP website (<http://ctep.cancer.gov>).

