3.5.5 Trametinib Dose Modification for Toxicities Not Specified in Subsequent Sections

Table 12 Trametinib Treatment Modification for Clinically Significant Toxicities Deemed Related to Trametinib

(This section is not for specific AEs such as hypertension, rash, ejection fraction changes, pneumonitis, diarrhea, liver chemistry, or visual changes. Refer to other sections for these specific AEs).

CTCAE v4 Grade	Management Guideline	Dose Modification
Grade 1	Monitor as clinically indicated. Provide supportive care according to institutional standards.	Continue trametinib at current dose level.
Grade 2 (tolerable)		
 Interrupt treatment until resolution to grade 1 or baseline. Upon resolution, restart treatment at current dose level.
Grade 2 (intolerable) and Grade 3		
 Interrupt treatment until resolution to grade 1 or baseline. Upon resolution to baseline or grade 1, restart with one level of dose reduction. If the Grade 3 toxicity recurs, interrupt trametinib; When toxicity resolves to Grade 1 or baseline, restart trametinib reduced by another dose level.
Grade 4		
If event resolves to grade 1 or baseline discuss potential continuation of trametinib with the subprotocol Study Chair; if continuation of treatment agreed then restart trametinib at dose reduced by one dose level.
 
If event does not resolve, permanently discontinue trametinib.

Trametinib should be discontinued if treatment delay is ≥ 14 days due to toxicities. If the investigator concludes that continued trametinib will benefit a patient, the subprotocol Study Chair may be consulted for the possibility of resuming trametinib, provided that toxicities have resolved to baseline or grade 1.

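### Table 4 lets trametinib restart after a Grade 4 visual event without recovery, although it requires recovery to grade 1 or lower after Grade 2-3

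*Protocol*

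**What the plan says.** Section 3.4.4 of the Protocol covers visual changes considered related to study treatment. Table 4 is organised by CTCAE grade, and trametinib is held for Grade 2, 3 and 4 events.

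- **Grade 2-3 row.** With RPED and RVO excluded, the instruction is to "restart trametinib at same dose level after visual AE is ≤ grade 1". Trametinib is discontinued if there is no recovery within 4 weeks.
- **Grade 4 row.** Immediate ophthalmology consultation and an SAE report are required, and a diagnosis of RPED or RVO means permanent discontinuation. Otherwise: "If RPED and RVO excluded, may restart trametinib at same or reduced dose after discussion with the subprotocol Study Chair".

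The NOTE at the head of Section 3.4 sets a default for long holds: "Patients who interrupt trametinib for > 2 weeks will be removed from this subprotocol". It exempts, among others, interruptions for "visual changes or RPED with subsequent recovery as described in corresponding tables below".

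**The concern.** Both rows deal with the same situation: drug held, RPED and RVO ruled out, and a decision to be made on resuming. The milder grades must recover first. The most severe grade need not, because its hold ends on a discussion.

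What is at stake is patient safety. These are drug-related events, and the Grade 4 row allows re-exposure at the unreduced dose. A dose-modification table is there so that the minimum condition for re-exposure does not rest on individual judgement. Here that minimum is absent for the grade where it matters most.

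**Working it through.** No arithmetic applies, so the check is a comparison of text in two steps.

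**Step 1: the two rows of Table 4, with RPED and RVO excluded**

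| | Grade 2-3 | Grade 4 |
|---|---|---|
| Trametinib held | Yes | Yes |
| Recovery needed before restart | Grade 1 or lower | None stated |
| Time limit in the row | 4 weeks, then discontinue | None stated |
| Study Chair discussion | Not required | Required |
| Restart dose | Same | Same or reduced |

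The Grade 4 row is stricter in other respects: it requires SAE reporting, uses permissive wording, offers a dose reduction, and stops treatment permanently for RPED. None of these makes recovery a condition of restart.

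**Step 2: does another provision supply the condition?**

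1. *Table 12 (Section 3.5.5).* Its Grade 4 row requires resolution to grade 1 or baseline, a Chair discussion and a one-level dose reduction. The scope note rules it out here: "This section is not for specific AEs such as hypertension, rash, ejection fraction changes, pneumonitis, diarrhea, liver chemistry, or visual changes".
2. *Closing paragraph of Section 3.5.5.* It allows the "possibility of resuming trametinib, provided that toxicities have resolved to baseline or grade 1", but it sits in the same excluded section and concerns delays of 14 days or more.
3. *Table 5.* It requires improvement to grade 1 or lower before restart, but covers RPED only and has no Grade 4 row.
4. *NOTE in Section 3.4.* It limits the length of a hold and sets no condition for a restart within 2 weeks. Its visual exemption depends on a recovery described in the tables. The Grade 4 row describes none, so an unrecovered Grade 4 patient stays subject to removal after more than 2 weeks.
5. *Section 3.4.2.* Its opening condition, "If an AE resolves to grade 1 or lower (or baseline) and remains grade 1 or lower at the reduced dose level", governs raising the dose again after a reduction. It does not govern restart after a hold.
6. *Section 3.1.* Treatment stops for intolerable toxicity. This is a general judgement with no recovery grade.
7. *Section 3.7.* Treatment stops for unacceptable toxicity, or when the protocol's constraints harm the patient. This too has no recovery grade.

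Provisions checked: 7. Provisions supplying a recovery condition for this case: 0.

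**Consequence.** During the first 2 weeks of a hold, restarting at the same dose with the Grade 4 visual event unresolved complies with Table 4 once the Chair has been consulted. Doing the same during an unresolved Grade 2 event breaches the Grade 2-3 row.

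**The case against.** **The rows use different gates.** The Grade 2-3 row is an instruction that the site carries out alone, so it needs a fixed threshold. The Grade 4 row authorises nothing automatically and replaces the threshold with case-by-case review by the Study Chair. Table 7 likewise leaves rechallenge after liver stopping criteria to Chair approval with no recovery grade, so the pattern could be deliberate. This has weight, and Table 4 is not unique in the protocol. But a Chair discussion does not imply recovery. Table 2 (asymptomatic LVEF decrease), Table 6 (Grade 3 pneumonitis), Table 8 (QTc) and Table 12 (Grade 4) each state both a recovery condition and Chair involvement.

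**The rows might apply to the current grade.** An event still at Grade 4 would then be held, and one that had improved to Grade 2-3 would fall under the row requiring grade 1 or lower. The text does not compel this reading. If adopted, it leaves the Grade 4 restart clause either without effect or as permission to restart while still at Grade 4.

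**Exposure is very narrow.** This stands. It takes a related Grade 4 visual event, RPED and RVO both excluded, no recovery, no more than 2 weeks of hold, an investigator who wants to restart, and a Chair who does not object. A careful Chair would probably refuse, and the general stops in Sections 3.1 and 3.7 may also prevent it. These points limit the importance of the finding but do not correct the text.

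**Conclusion.** The concern holds. With RPED and RVO excluded, Table 4 requires recovery to grade 1 or lower before restart for Grade 2-3 and states no recovery requirement for Grade 4. Nothing else in the Protocol fills the gap.

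The number of patients affected will be small and cannot be estimated: the accrual goal is 35, and the Protocol gives no rate for Grade 4 visual events with RPED and RVO excluded. The window for restart without recovery is at most 2 weeks of hold. That limit assumes the Section 3.4 NOTE is read as above, with its visual exemption unavailable to an unrecovered Grade 4 patient. No endpoint, sample size or analysis depends on this point.

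It should be corrected as a safety rule. The conclusion rests on the inversion inside Table 4 and does not claim that a hold limit is missing.

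**What to change.** Change the Grade 4 cell of Table 4 so that it says, in substance:

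> With RPED and RVO ruled out, trametinib may be resumed, at the same or a reduced dose, only once the visual AE is grade 1 or lower and the subprotocol Study Chair has been consulted. Without that recovery, stop trametinib permanently. The removal after more than 2 weeks in the Section 3.4 NOTE applies.

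The last sentence is needed because, once the cell describes a recovery, the NOTE's visual exemption could be read as lifting the 2-week removal for Grade 4. The 4 weeks used for Grade 2-3 should not be carried over by default; if the medical team prefers that limit, the cell should state it instead. The option to restart at the same dose is left as it is. Table 12 requires a one-level reduction after Grade 4, so the team may wish to consider that separately.

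The cost is one table cell in the next amendment, with no added procedures or patients. The one loss is the discretionary restart for a rare patient whose Grade 4 visual event has not recovered, an option the Protocol already denies for Grades 2-3.

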3.4.5 Pneumonitis Management Guidelines

Pneumonitis has been observed in subjects receiving trametinib. To reduce the risk of pneumonitis, subjects will be monitored closely for symptoms, evaluated with imaging and functional tests. Dose modification and supportive care guidelines for pneumonitis are described (see Table 6).

Table 6 Pneumonitis Guidelines for Trametinib

CTCAE Grade	Adverse Event Management	Action and Dose Modification
Grade 1	
 CT scan (high-resolution with lung windows) recommended Clinical evaluation and laboratory work-up for infection Monitoring of oxygenation via pulse-oximetry recommended Consultation with pulmonologist recommended 	
 Continue trametinib at current dose
Grade 2	
 CT scan (high-resolution with lung windows) recommended Clinical evaluation and laboratory work-up for infection Consult pulmonologist Pulmonary function tests -if < normal, repeat every 8 weeks until ≥ normal Bronchoscopy with biopsy and/or BAL recommended Symptomatic therapy including corticosteroids if clinically indicated 	
 Interrupt trametinib until recovery to grade ≤ 1 Restart treatment with trametinib reduced by one dose level Escalation to previous dose level after 4 weeks and consultation with the subprotocol Study Chair possible If no recovery to grade ≤ 1 within 2 weeks, permanently discontinue trametinib
Grade 3	
 Same as Grade 2 	
 Interrupt trametinib until recovery to grade ≤ 1 After consultation with the subprotocol Study Chair, treatment with trametinib may be restarted reduced by one dose level If no recovery to grade ≤ 1 within 2 weeks, permanently discontinue trametinib
Grade 4	
 Same as Grade 2 	
 Permanently discontinue trametinib

Abbreviations: BAL= bronchioalveolar lavage; CT = computed tomography; CTCAE = Common Terminology Criteria for Adverse Events

3.5 Dose Modifications for Trametinib and supportive care

Rev. 12/16

3.5.1 Trametinib Dose Modification for Liver Chemistry Changes

Table 7: Trametinib Dose Modification for Liver Function Test Abnormalities

Event	Treatment modifications and assessment/monitoring

ALT \geq 3x ULN but < 5x ULN and TB < 2x ULN, without symptoms considered related to liver injury or hypersensitivity and who can be monitored weekly for 4 weeks
	
 • May continue study drug. • Report as SAE if CTEP-AERS reporting criteria is met. • If liver chemistry stopping criteria are met any time, proceed as described below. 
MONITORING: Repeat LFT (ALT, AST, ALK, bilirubin) until they return to normal/baseline or stabilise (LFT may be every 2 weeks after 4 weeks if ALT < 3x ULN and TB < 2 ULN). If baseline ALT and Tbili already meet these criteria, then monitoring is required only if ALT or TB rises after initiation of study therapy.


Criteria for discontinuing study drug: When any of the liver stopping criteria below is met, discontinue trametinib
 
 1. ALT \geq3xULN and bilirubin \geq 2x ULN or >35% direct bilirubin ^{1,2} 2. ALT \geq 3xULN and INR >1.5, if INR measured² (INR threshold does not apply if subject is on anticoagulant) 3. ALT \geq 5x ULN 4. ALT \geq 3x ULN persists for \geq 4 weeks. However, if ALT was elevated 3-5x at baseline due to liver mets, then this criteria should not be used for treatment discontinuation UNLESS the ALT improves to < 3x ULN and then subsequently rises. 5. ALT \geq 3x ULN and cannot be monitored weekly for 4 weeks. However, if ALT was elevated 3-5x at baseline due to liver mets, then this criteria should not be used for treatment discontinuation UNLESS the ALT improves to < 3x ULN and then subsequently rises. 6. ALT \geq 3x ULN associated with symptoms³ (new or worsening) believed to be related to liver injury or hypersensitivity 	
 • Immediately discontinue study treatment. • Do not restart/rechallenge unless approved by the subprotocol Study Chair. [• Report as SAE if: 1) CTEP-AERS reporting criteria are met, or 2) patients meet criteria 1-2. • Perform liver event ASSESSMENT AND WORKUP (see below). • Monitor the subject until liver chemistries resolve, stabilize, or return to baseline (see MONITORING below). • If applicable, provide details on required follow up assessments (e.g., follow up for overall survival or disease recurrence or progression). [Do not include for single-dose studies] 
MONITORING: In patients stopping for criteria 1-2 (with abnormal TB and INR, indicating potentially more significant liver toxicities):
 
 • Repeat liver chemistries (ALT, AST, ALK, bilirubin) and perform liver event follow-up assessments within 24 hours. • Monitor subjects twice weekly until LFT return to normal/baseline or stabilize. • A specialist or hepatology consultation is recommended. 
In patients stopping for criteria 2-6:
 
 • Repeat LFT and perform liver event follow up assessments within 24-72 hrs • Monitor subjects weekly until LFTs return to normal/baseline or stabilize. 
ASSESSMENT and WORKUP:
 
 • Viral hepatitis serology.⁴ • Serum CPK and LDH. • Fractionate bilirubin, if total bilirubin \geq 2x ULN. • CBC with differential to assess eosinophilia. • Record clinical symptoms of liver injury, or hypersensitivity on AE CRF. • Record concomitant medications (including acetaminophen, herbal

Event	Treatment modifications and assessment/monitoring
	
remedies, other over the counter medications).
 
 • Record alcohol use. 
Additional work up for patient stopping for criteria 1-2 (with abnormal TB and INR, indicating potentially more significant liver toxicities):
 
 • Anti-nuclear antibody, anti-smooth muscle antibody, Type 1 anti-liver kidney microsomal antibodies, and quantitative total immunoglobulin G (IgG or gamma globulins). • Serum acetaminophen adduct HPLC assay (in subjects with likely acetaminophen use in the preceding). • If there is underlying chronic hepatitis B (e.g. positive hepatitis B surface antigen): quantitative hepatitis B DNA and hepatitis delta antibody.⁵ • Liver imaging (ultrasound, MRI, CT) and /or liver biopsy.

Footnotes:
 
 1. Serum bilirubin fractionation should be performed if testing is available. If serum bilirubin fractionation testing is unavailable, record presence of detectable urinary bilirubin on dipstick, which indicates direct bilirubin elevations and suggesting liver injury. 2. All events of ALT $\geq 3 \times$ ULN and bilirubin $\geq 2 \times$ ULN (>35% direct bilirubin) or ALT $\geq 3 \times$ ULN and INR > 1.5 (if INR measured) may indicate severe liver injury (possible "Hy's Law"). INR measurement is not required, and the threshold value stated will not apply to subjects receiving anticoagulants. 3. New or worsening symptoms believed to be related to liver injury (such as fatigue, nausea, vomiting, right upper quadrant pain or tenderness, or jaundice) or believed to be related to hypersensitivity (such as fever, rash or eosinophilia) 4. Includes: Hepatitis A IgM antibody; Hepatitis B surface antigen and Hepatitis B Core Antibody (IgM); Hepatitis C RNA; Cytomegalovirus IgM antibody; Epstein-Barr viral capsid antigen IgM antibody (or if unavailable, obtain heterophile antibody or monospot testing); Hepatitis E IgM antibody 5. If hepatitis delta antibody assay cannot be performed, it can be replaced with a PCR of hepatitis D RNA virus (where needed) (Le Gal et al., 2005). 	

Rev. 12/16

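### Protocol Table 7 puts liver stopping criterion 2 (ALT ≥ 3x ULN with INR > 1.5) under both monitoring schedules; the second heading should read criteria 3-6 only

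*Protocol*

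**What the plan says.** Table 7 in Protocol Section 3.5.1 sets out six liver stopping criteria. Criterion 1 is ALT ≥ 3x ULN with raised bilirubin. Criterion 2 is ALT ≥ 3x ULN with INR > 1.5, where INR was measured and the patient is not on an anticoagulant. Criteria 3 to 6 concern the level of ALT, its persistence, the ability to monitor it, and symptoms. One criterion is enough to stop: "When any of the liver stopping criteria below is met, discontinue trametinib".

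Under MONITORING the table gives two schedules.

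- Intensive: "In patients stopping for criteria 1-2 (with abnormal TB and INR, indicating potentially more significant liver toxicities"). Sites must repeat chemistries and "perform liver event follow-up assessments within 24 hours", then "Monitor subjects twice weekly until LFT return to normal/baseline or stabilize". In addition, "A specialist or hepatology consultation is recommended".
- Less intensive: "In patients stopping for criteria 2-6". Sites "Repeat LFT and perform liver event follow up assessments within 24-72 hrs", then "Monitor subjects weekly until LFTs return to normal/baseline or stabilize". No consultation is listed.

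The table has no rule on which schedule applies when a patient falls under both headings.

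**The concern.** Criterion 2 is named in both headings, and the two schedules differ in the timing of the first recheck, the frequency of monitoring and the consultation. Footnote 2 to the same table treats ALT ≥ 3x ULN with INR > 1.5 as a possible Hy's Law event, a sign of potentially severe liver injury. As printed, a patient in one of the two most serious categories is therefore also listed under the weaker follow-up.

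What is at stake is how closely such a patient is followed after trametinib is stopped. Stopping the drug, SAE reporting, the general work-up and the additional work-up do not depend on this heading.

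**Working it through.** The protocol gives no figure to reproduce on this point. The check compares the criteria under each heading, then asks which heading the rest of the table supports.

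**1. Overlap.** The intensive heading covers {1, 2} and the less intensive heading covers {2, 3, 4, 5, 6}. They share {2}, so 1 of the 6 criteria has two schedules. If the second heading began at 3, the sets {1, 2} and {3, 4, 5, 6} would share nothing and together cover all six.

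**2. What the overlap means for a patient who meets criterion 2.**

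| Item | Intensive schedule | Less intensive schedule |
|---|---|---|
| First recheck | by 24 h | 24 to 72 h |
| Monitoring | twice weekly | weekly |
| Specialist or hepatology consultation | recommended | not listed |

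The latest permitted first recheck differs by 72 − 24 = 48 h. Visit frequency differs by a factor of 2.

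**3. Which heading is wrong.** Three other places in Table 7 put criterion 2 with criterion 1:

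- the SAE rule, which singles out criteria 1 and 2;
- the additional work-up, reserved for criteria 1 and 2;
- footnote 2, which names both combinations as possible Hy's Law.

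The intensive heading agrees, because it refers to abnormal INR and INR appears in no criterion but the second. Outside the table, Section 3.2.1 pairs ALT with bilirubin and ALT with INR as the two liver triggers for expedited reporting. Only the less intensive heading departs from this grouping.

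**4. Whether changing the digit alone is enough.** Any one criterion stops the drug, so several can be met together. A patient with ALT ≥ 5x ULN and INR > 1.5 meets criteria 2 and 3. With a second heading of 3-6, that patient would still be under both headings. Counting the combinations of labels shows how far each wording goes.

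- Non-empty combinations of six criteria: 2^6 − 1 = 63.
- Under both headings as printed: 2^5 = 32 combinations that contain criterion 2, plus 2^4 − 1 = 15 that contain criterion 1, not 2, and at least one of 3 to 6. Total 32 + 15 = 47.
- Under both with a second heading of 3-6: (2^2 − 1) × (2^4 − 1) = 3 × 15 = 45. Only {2} and {1, 2} are resolved.
- With a second heading of 3-6 only: the 15 combinations made up solely of 3 to 6 take the less intensive schedule and the other 63 − 15 = 48 take the intensive one. None falls under both and none under neither.

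These are combinations of labels, not patients. The criteria are not independent and some combinations may hardly occur. The count shows only that the word *only* is needed for each combination to have a single schedule.

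**5. How many patients.** The protocol gives no expected number. The Schema states an accrual goal of 35. Footnote 2 says that INR need not be measured and that its threshold is not applied to patients on anticoagulants. INR is not in the scheduled chemistry list of Section 4.1, footnote B. The number is therefore likely to be very small.

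**The case against.** The strongest reply is that the two schedules can both be met. A recheck at 24 hours satisfies a 72-hour limit, and twice-weekly visits satisfy a weekly rule. A site that applies everything said about criterion 2 ends up on the intensive schedule. The intensive heading stands directly above the other and explains why criterion 2 belongs there. By then the patient is off drug, flagged for SAE reporting and due the extended work-up, and restarting needs Study Chair approval. The event is also rare. On this view the flaw is a numbering slip and *only* is a drafting preference, since clinicians would apply the stricter tier to a patient who meets several criteria.

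Much of this stands. The overlap is an internal inconsistency, most likely a slip, and its effect is limited. The label counts say nothing about frequency. But the protocol does not state that the stricter schedule prevails, and a site working from the second heading alone would be following printed text. *Only* is more than a preference, because without it a patient who meets criterion 1 or 2 together with any of 3 to 6 still has two schedules. That includes criterion 1 patients, for whom no INR is needed.

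**Conclusion.** The concern holds. Table 7 gives criterion 2 two incompatible minimum schedules, and the less intensive heading is the one in error. One criterion of six is affected, with a first recheck up to 48 hours later, half the visit frequency and no recommended consultation if the wrong heading is used. Under-monitoring would occur only at a site that applied the second heading without the first.

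The conclusion about which heading is wrong rests on the table's own grouping of criteria 1 and 2 and needs no outside source. That few patients would be affected is a judgement from the accrual goal and the limited INR testing, since the protocol gives no rate. Sample size, endpoints and analysis are not affected. It should be corrected because it is an operative safety instruction for a possible Hy's Law event.

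**What to change.** In Table 7, change the second MONITORING heading so that it applies to patients stopping for **criteria 3-6 only**. A patient who meets criterion 1 or 2, alone or with others, then follows the intensive schedule.

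No other edit is needed. The cost is one digit and one word, and it adds no procedure beyond those the intensive heading already requires.
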